6. DATA CONVENTIONS

The following analysis conventions will be used in the statistical analysis.

6.1. Definition of Baseline for Efficacy/Safety Variables

Unless otherwise specified, the Baseline assessment for all measurements will be the latest available valid measurement taken prior to the administration of investigational product.

6.2. Data Handling Convention for Efficacy Variables

Patients who are deemed NE according to RECIST version 1.1. or inevaluable by the composite response criteria will be considered as not reaching PR/CR in calculating ORR, i.e. they are not considered as responders in the numerator of ORR, but they are counted in the denominator of ORR.

6.3. Data Handling Convention for Missing Data

No missing data imputation is planned in this study unless specified otherwise.

For categorical variables, patients with missing data are not included in calculations of percentages unless otherwise specified. When relevant, the number of patients with missing data is presented.

Medication missing/partial dates

To determine whether a medication is prior, concomitant or post-treatment medication, the missing medication start date is estimated as early as possible up to date of the first study treatment, and the missing medication end date is estimated as late as possible. If the medication start date is missing, the onset day will not be imputed in medication listings.

Date of first / last study treatment

Date of first infusion is the first non-missing start date of dosing filled in the CRF “Investigational Product” module.

If a patient’s date of the last dose is totally missing or unknown, his/her last visit date will be substituted.

6.4. Unscheduled Assessments

Unscheduled visit measurements may be used to provide a measurement for a baseline or endpoint value if appropriate according to their definition. The measurements may also be used to determine abnormal laboratory or ECG values.

The determination of baselines and values at the end of treatment for both efficacy and safety variables will be based on scheduled available assessments and unscheduled available assessments.

Extra assessments (laboratory data or vital signs associated with non-protocol clinical visits or obtained in the course of investigating or managing adverse events) will be included in listings, but not by visit summaries except for the endpoint determination. If more than one laboratory value is available for a given visit, the first observation will be used in summaries and all observations will be presented in listings.

7. MULTIPLICITY CONSIDERATIONS

Adjustments to the significance level for the purposes of multiple testing are not applicable for this study. Statistical analyses of efficacy for each group will be conducted and reported separately; ie, efficacy results and clinical conclusions from one Group will not affect those of other Groups, and vice versa. Therefore, statistical control of overall type I error for the whole study is not planned. There is no multiplicity adjustment for secondary endpoint.

8. INTERIM ANALYSIS

Interim analysis for Group 2

At the time of the planned efficacy analysis for Group 1 (6 months after first dose of last patient), an interim analysis of efficacy for Group 2 patients will be performed in order to better assess the risks and benefits of cemiplimab in CSCC. This analysis will be restricted to Group 2 patients with potential for adequate follow up, defined as patients who have opportunity to receive approximately 9 months of study treatment at the time of the interim analysis.

For regions where alpha spending is not required: For this planned interim analysis, the ORR and associated 95% confidence interval will be summarized. As the primary objective of this the interim analysis is point estimation on ORR and characterizing the precision of point estimation, there is no hypothesis testing associated with this interim analysis. Also, no decisions will be made regarding study conduct associated with the interim analysis. Therefore, Type I error adjustment is not applicable for this planned interim analysis.

For regions where alpha spending is required: For this interim analysis on group 2 patients, two-sided alpha of 0.0001 will be allocated for interim analysis and two-sided alpha of 0.0499 will be preserved for the final analysis. Correspondingly, for the interim analysis of primary endpoint of ORR in group 2 patients, the precision of ORR will be estimated by adjusted and two-sided 99.99% exact confidence interval. The un-adjusted and two-sided 95% exact confidence interval will also be reported at the time of interim analysis. At the time of the final analysis for group 2 patients, both adjusted 95.01% and un-adjusted 95% exact confidence interval will be reported.

For other efficacy endpoints in group 2 patients, only two-sided 95% exact confidence interval will be presented both at the interim and at the final analysis.

Interim analysis for Group 6

Per sample size calculation, 167 patients are planned for Group 6. An interim analysis of Group 6 patients will be performed after the first 50% of patients have had the opportunity to be followed up for a minimum of 28 weeks (27 weeks for 3 tumor assessments + 1-week assessment window) or have reached the end of study. The interim analysis will include a minimum of 20 locally advanced CSCC patients. If 20 locally advanced patients are not yet enrolled in the set of the first 84 patients enrolled in Group 6, the interim analysis will be performed after 20 locally advanced CSCC patients have been enrolled and have had the opportunity to be followed for at least 28 weeks. All patients enrolled in Group 6 who have had the opportunity to be followed for at least 28 weeks will be included in the interim analysis.

For regions where alpha spending is not required: For this planned interim analysis, the ORR and associated 95% confidence interval will be summarized. As the primary objective of this interim analysis is point estimation on ORR and characterizing the precision of point estimation, there is no hypothesis testing associated with this interim analysis. Therefore, Type I error adjustment is not applicable for this planned interim analysis.

For regions where alpha spending is required: The overall type I error rate for analyses of the primary endpoint of ORR is controlled at a 2-sided alpha of 0.05 using the O'Brien-Fleming spending function. [Table 1](#) demonstrates the bound and boundary properties for ORR hypothesis testing at interim and final analyses, assuming interim analysis was performed at 50% of

enrollment. The table will be updated using the actual number of patients included in the interim and final ORR analysis.

Table 1: Alpha Spending for Analysis of ORR on Group 6 Patients

Analysis		Value
Interim Analysis ^a	Z	2.9626
	α (2-sided ^a)	0.0031
Final Analysis	Z	1.9686
	α (2-sided)	0.0490

^a As a 2-sided test is used at interim, the superiority or futility of cemiplimab treatment will be claimed if the statistical boundary is crossed.

For the interim analysis of ORR, the precision of ORR will be estimated by adjusted 2-sided 99.69% exact confidence interval. The un-adjusted 2-sided 95% exact confidence interval will also be reported at the time of interim analysis. The ORR of 28% for Group 6 will be excluded using the lower limit of 99.69% exact CI if the observed ORR is 44.1% or more (Table 2).

At the time of the final analysis, both adjusted 95.10% and un-adjusted 95% exact confidence interval will be reported. The confidence level will be updated using the actual number of patients included in the interim and final ORR analysis.

For other efficacy endpoints in Group 6 patients, only a 2-sided 95% confidence interval will be presented both at the interim and at the final analysis.

Table 2: Binomial Exact Confidence Intervals for Observed ORR in Group 6

Analysis	Two-sided Exact CI	N	Number of Responders	Observed ORR	Lower Bound	Upper Bound
Interim	99.69%	84	37	44.1%	28.4%	60.6%
Final	95.10%	167	59	35.3%	28.1%	43.1%

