9.1. Statistical Hypothesis

For the primary endpoint of ORR, the following null hypothesis and alternative will be tested for Groups 1, 2, 3, 4, and 6, respectively.

Group 1: H_0 : ORR = 15% vs. H_1 : ORR \neq 15%

Group 2: H_0 : ORR = 25% vs. H_1 : ORR \neq 25%

Group 3: H_0 : ORR = 15% vs. H_1 : ORR \neq 15%

Group 4: H_0 : ORR = 20% vs. H_1 : ORR \neq 20%

Group 6: H_0 : ORR = 28% vs. H_1 : ORR \neq 28%

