Table 23, Table 24, and Table 25 provide the 95% confidence intervals for observed ORRs at interim analysis for the advanced CSCC patients and 2 subgroups of Group 6: metastatic and locally advanced CSCC separately. The interim analysis for Group 6 is based on all advanced CSCC patients in the Group 6 interim analysis. Subgroup analyses are descriptive.

Table 23: The Binomial Exact Confidence Intervals for Observed ORR in Advanced CSCC Patients at Interim Analysis of Group 6 (N=84)

Number of Responders	ORR (N=84)	99.69% CI (%)	95% CI (%)
30	35.7%	(21.2, 52.4)	(25.6, 46.9)
31	36.9%	(22.2, 53.6)	(26.6, 48.1)
32	38.1%	(23.2, 54.8)	(27.7, 49.3)
33	39.3%	(24.2, 56.0)	(28.8, 50.5)
34	40.5%	(25.2, 57.1)	(29.9, 51.7)
35	41.7%	(26.3, 58.3)	(31.0, 52.9)
36	42.9%	(27.3, 59.5)	(32.1, 54.1)
37	44.0%	(28.4, 60.6)	(33.2, 55.3)

Table 24: The Binomial Exact Confidence Intervals for Observed ORR in Metastatic CSCC Patients at Interim Analysis (N=64)

Number of Responders	ORR (N=64)	95% CI (%)
23	35.9%	(24.3, 48.9)
24	37.5%	(25.7, 50.5)
25	39.1%	(27.1, 52.1)
26	40.6%	(28.5, 53.6)
27	42.2%	(29.9, 55.2)
28	43.8%	(31.4, 56.7)
29	45.3%	(32.8, 58.3)

Table 25: The Binomial Exact Confidence Intervals for Observed ORR in Locally Advanced CSCC Patients at Interim Analysis (N=20)

Number of Responders	ORR (N=20)	95% CI (%)
6	30%	(11.9, 54.3)
7	35%	(15.4, 59.2)
8	40%	(19.1, 63.9)
9	45%	(23.1, 68.5)

SIGNATURE OF SPONSOR’S RESPONSIBLE OFFICERS

(Medical/Study Director, Regulatory Representative, Clinical Study Team Lead, and Biostatistician)

To the best of my knowledge, this protocol accurately describes the conduct of the study.

Study Title: A Phase 2 Study of REGN2810, a Fully Human Monoclonal Antibody to Programmed Death-1 (PD-1), in Patients with Advanced Cutaneous Squamous Cell Carcinoma

Protocol Number: R2810-ONC-1540

Protocol Version: R2810-ONC-1540 Amendment 9

See appended electronic signature page

Sponsor’s Responsible Medical/Study Director:

See appended electronic signature page

Sponsor’s Responsible Regulatory Liaison:

[figure not shown]
See appended electronic signature page

Sponsor’s Responsible Clinical Study Team Lead:

See appended electronic signature page

Sponsor’s Responsible Biostatistician:

Signature Page for VV-RIM-00165169 v2.0

ESig Approval	 09-Sep-2021 00:58:33 GMT+0000
---------------	---

ESig Approval	 09-Sep-2021 12:35:22 GMT+0000
---------------	---

ESig Approval	 09-Sep-2021 14:40:24 GMT+0000
---------------	---

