5.8.1. Analysis of Primary Efficacy Variable

The ORR according to central review will be summarized by group and the corresponding 2-sided 95% exact binomial confidence intervals will be derived using the Clopper Pearson method (Clopper, 1934). BOR will also be summarized by group.

The primary analysis of efficacy is based on the exact binomial confidence interval approach of ORR. If the lower limit of 95% confidence interval of observed ORRs excludes 15% for Group

1 and Group 3, excludes 25% for Group 2, exclude 20% for Group 4, or exclude 28% for Group 6, the study treatment is deemed effective for that group, respectively.

In addition, ORR along with two-sided 95% exact binomial confidence intervals for all patients treated with cemiplimab will be presented. ORR in patients whose CSCC disease has been confirmed by central pathology review will also be summarized.

A sensitivity analysis will be performed for ORR using patients who received at least one dose of cemiplimab.

For Group 6 patients who opt to switch to SC cemiplimab, efficacy data per central review will be censored at the first SC dose. Because Group 6 patients are only allowed to switch to SC cemiplimab after completing at least 27 weeks on study (3 tumor assessments after baseline), which is the pre-specified timepoint for primary efficacy analyses in Group 6, switching to SC dosing will have no impact on the primary efficacy analysis for Group 6.

The primary endpoint of ORR will also be summarized by pooling the objective response observed in CSCC patients in this study with object response data of CSCC patients in Regeneron study R2810-ONC-1423 to satisfy regulatory requirements from certain regions. Details will be provided in separate SAP for integrated efficacy analysis.

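### The SAP prints the Group 6 interim threshold for 37 of 84 responders as 44.1%; it is 44.0%, as protocol Table 23 shows

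*SAP*

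**What the plan says.** Protocol Section 9.1 sets the Group 6 null ORR at 28%. In regions that require alpha spending, SAP Section 8 applies an O'Brien-Fleming spending function. SAP Table 1 gives an interim boundary of Z = 2.9626, a two-sided alpha of 0.0031. SAP Section 8 then states that "the precision of ORR will be estimated by adjusted 2-sided 99.69% exact confidence interval", and that the lower limit of that interval excludes 28% "if the observed ORR is 44.1% or more", citing SAP Table 2.

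The interim row of SAP Table 2 reads "Interim 99.69% 84 37 44.1% 28.4% 60.6": confidence level, number of patients, responders, observed ORR, lower bound and upper bound.

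Protocol Appendix 10, Table 23 covers the same interim analysis with 84 patients. Its row for the same result is "37 44.0% (28.4, 60.6) (33.2, 55.3", where the first interval is at 99.69% and the second at 95%. The row one responder lower is "36 42.9% (27.3, 59.5) (32.1, 54.1".

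SAP Section 8 adds that the boundary table and the confidence levels will be updated to the number of patients actually analysed.

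**The concern.** The two documents give the same count, the same number of patients and the same interval, but different percentages. The SAP sentence is the only place where the interim criterion is expressed as a percentage cut-off, and the footnote to SAP Table 1 ties a claim of superiority or futility to crossing the boundary. A pre-specified cut-off should agree with the table that it cites.

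An analyst who programmed the sentence as a comparison of the unrounded proportion with 0.441 would find that 37/84 falls short, although SAP Table 2 shows that result as excluding 28%. The percentage and the count would then differ by one responder.

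**Working it through.** **Inputs.** Null ORR 28% (protocol Section 9.1). Interim number of patients 84, responders 37, printed ORR 44.1%, bounds 28.4% and 60.6% (SAP Table 2). Boundary Z = 2.9626, alpha 0.0031, confidence level 99.69% (SAP Section 8 and Table 1). Design alternative 40% (SAP Section 2.2). For the interval method, SAP Section 5.8.1 says that "2-sided 95% exact binomial confidence intervals will be derived using the Clopper Pearson method"; I used the same method at 99.69%.

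**Confidence level.** Two-sided alpha = 2 × (1 − Φ(2.9626)) = 0.00305, which rounds to 0.0031, and 1 − 0.0031 = 99.69%. This reproduces.

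**Interval bounds and critical count.** For x responders out of n, with α = 0.0031, the lower limit is the α/2 quantile of Beta(x, n − x + 1) and the upper limit is the 1 − α/2 quantile of Beta(x + 1, n − x). The upper tail is P(X ≥ x) for X binomial with n = 84 and p = 0.28.

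| Responders | ORR (x/84) | 99.69% lower | 99.69% upper | Upper tail at 28% | Tail doubled | Excludes 28%? |
|---|---|---|---|---|---|---|
| 36 | 42.857% | 27.31% | 59.46% | 0.00247 | 0.0049 | no |
| 37 | 44.048% | 28.37% | 60.61% | 0.00120 | 0.0024 | yes |
| 38 | 45.238% | 29.43% | 61.75% | 0.00056 | 0.0011 | yes |

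The bounds for 36 and 37 match protocol Table 23, and those for 37 match SAP Table 2. The smallest count whose interval excludes 28% is 37. The doubled tail agrees: 0.0024 is below 0.0031 and 0.0049 is above it.

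**The percentage.** 37 ÷ 84 = 0.440476, or 44.048%, which is 44.0% to one decimal. The next possible value is 38 ÷ 84 = 45.238%, so no count out of 84 gives 44.1%. Rounding twice (44.048 to 44.05, then to 44.1) would produce the printed figure, but the documents do not say how it arose.

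**The final row, for comparison.** 59 ÷ 167 = 35.33%, printed as 35.3%. The 95.10% interval is 28.07% to 43.12%, printed as 28.1% and 43.1%. That row is correct.

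**What a literal reading would change.** Only the outcome of exactly 37 responders is affected.

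- At a true ORR of 40%, the probability of crossing the upper boundary is 25.8% with a cut-off of 37 and 19.2% with 38, a difference of 6.6 percentage points.
- At 28%, the one-sided type I error is 0.0012 with 37 and 0.0006 with 38, so the literal reading errs in the conservative direction.

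**Dependence on the number of patients.** With the 99.69% level held fixed (an assumption, since it is to be updated), the smallest count that excludes 28% is 38 of 85 (44.7%), 38 of 87 (43.7%), 39 of 90 (43.3%) and 41 of 95 (43.2%). No single percentage, 44.0% included, carries over to another interim size.

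**The case against.** A reader might infer that the SAP's rule rejects 37/84 and requires 38 responders. The documents do not support that, for three reasons.

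- The operative criterion is the confidence limit. SAP Section 5.8.1 judges efficacy by whether the lower limit excludes 28%, and the interim sentence in Section 8 is built on the lower limit of the 99.69% interval. The percentage only translates that rule.
- The sentence gives a sufficient condition. Any ORR at or above 44.1% with 84 patients does exclude 28%, and nothing says that a lower one fails.
- The sentence cites SAP Table 2, where 44.1% is the label for 37/84 with a lower bound of 28.4%. Protocol Table 23 also shows 37 as the first count whose lower limit exceeds 28%.

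The figure also belongs to a planned size of 84. The interim may move until 20 locally advanced patients have enough follow-up, everyone in Group 6 with that follow-up is included, and the boundary is to be recalculated. Where alpha spending is not required, there is no interim hypothesis test.

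Finally, the correction may have no practical effect. This SAP was approved in December 2023 and follows Amendment 9, which protocol Section 1.2.1 says would be implemented only after the data cut for the primary analyses. The interim had probably been done by then, though the documents give no date for it.

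All of this stands and limits the importance of the point. None of it makes 44.1% a correct figure, and the conflict with protocol Table 23 remains.

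**Conclusion.** Wrong as written, of minor severity. In two places the current SAP prints a percentage that its own count does not give and that the protocol contradicts. The error is 0.1 percentage point after rounding (44.1% against 44.0%). The critical count, the interval bounds, the confidence level and the final-analysis row are all correct, so neither the design nor the alpha spending is in question.

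The error could alter a conclusion only if the interim analysis had exactly 84 patients and exactly 37 responders, and the printed percentage were applied to the unrounded proportion instead of the confidence limit. The calculation assumes Clopper-Pearson limits at 99.69%, which reproduce the published bounds.

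**What to change.** In SAP Section 8 and in the interim row of SAP Table 2, change 44.1% to 44.0%.

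Reword the sentence in Section 8 so that the confidence limit is plainly the rule, for example: *an ORR of 28% is excluded if the lower limit of the adjusted exact confidence interval exceeds 28% (at N = 84: 37 or more responders, 44.0%), to be recalculated for the actual interim number of patients.* The count should stay in parentheses as an illustration, so that a threshold specific to 84 patients is not fixed in a rule that is to be updated.

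The cost is two figures and one sentence in the SAP. Protocol Table 23 needs no change, and no calculation, sample size or alpha allocation is affected.

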9. SOFTWARE

All statistical analyses will be done using SAS Version 9.4 or above.

11. APPENDIX

11.1. Summary of Statistical Analyses

Efficacy Analysis:

Endpoint	Analysis Populations	Primary Analysis	Statistical Method	Supportive Analysis	Subgroup Analysis	Other Analyses
Primary Endpoint						
ORR	FAS	Proportion of patients with best overall response of CR or PR (central review)	95% exact binomial confidence interval using Clopper-Pearson method	Exact binomial test p-value	Yes	Yes
Secondary Endpoints						
ORR	FAS	Proportion of patients with best overall response of CR or PR (investigator review)	95% exact binomial confidence interval using Clopper-Pearson method	Exact binomial test p-value	No	No
Duration of response	Patients with best overall response of CR/PR in FAS	From the time measurement criteria are first met for CR/PR (whichever is first recorded) until the first date of recurrent or progressive disease (radiographic), or death due to any cause.	Kaplan-Meier method and descriptive statistics	No	Yes	No
Progression-free survival	FAS	From the start of treatment until the first date of recurrent or progressive disease (radiographic), or death due to any cause.	Kaplan-Meier method	No	No	No
Overall survival	FAS	From the start of treatment until death due to any cause.	Kaplan-Meier method	No	No	No
Quality of life	FAS	Changes scores from day 1 of EORTC-QLQ-C30	Descriptive statistics and longitudinal plots	No	No	No

Safety Analyses:

Endpoint	Analysis Populations	Primary Analysis	Statistical Method	Supportive Analysis	Subgroup Analysis	Other Analyses
Adverse Events	SAF	Percent of patients by system organ class and PT	Descriptive Statistics	No	No	No

Signature Page for VV-RIM-00330503 v1.0

Approval/eSignature	 12-Dec-2023 22:56:28 GMT+0000
---------------------	---

Approval/eSignature	 13-Dec-2023 02:12:18 GMT+0000
---------------------	---

Approval/eSignature	 13-Dec-2023 03:02:56 GMT+0000
---------------------	---

Signature Page for VV-RIM-00330503 v1.0 Approved
